1. STUDY RATIONAL

Diabetes is one of the largest medical challenges facing the world today. 12% of the world's health budget is spent on diabetes, that is USD 673 billion (Euros 585 billion). It is estimated that a lower limb is amputated due to diabetes every 30 sec. on a global scale, and it is known that 85% of all amputations are performed due to a diabetic ulcer¹. In Denmark 320.000 citizens has a diabetes diagnosis, an additional 200.000 are estimated to have diabetes unknowingly, and 750.000 to have the pre-stages of diabetes². These numbers have doubled in the past ten years and are estimated to cost DKK 86 million a day (or Euros 11.6 million a day)¹. One of the complications to diabetes is the "diabetic foot syndrome", which is a result of neurological abnormalities, vascular complications or a combination of the two. Knowledge about the causes of the disease has been gathered since the late nineteenth century³. In recent years, preventive therapy has been the focus of treatment, resulting in several national and international guidelines^{4,5,6}. Focus has been on education in self-care and awareness of risk factors, combined with "Foot-at-Risk" evaluation⁷, at least once a year and off-loading therapy crafted and applied by specialized personnel^{3,4}.

Steno Diabetes Center Copenhagen, University of Copenhagen, Denmark is a highly-specialized treatment facility focusing on the patient with diabetes. In spite of optimized treatment for patients with diabetes, and the fact that incidence of first time ulcers in patients with type 1 and 2 diabetes is declining, the incidence of first time ulcers is still 2.6 and 8.7 per. 1000 patient years for type 1 and 2, respectively⁸. Diabetic foot ulcers have a known association with increased mortality, morbidity and economic burden^{9,10,11}, at the same time most amputations in patients with diabetes are preceded by an ulcer¹².

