4. AIM

The aim of the RCT is to evaluate the effect of needle tenotomy when treating impending ulcers associated with hammer, mallet and claw toe deformities.

The study is designed as a prospective RCT comparing needle tenotomy with conservative treatment, for patients with deformities and impending ulcers associated with the three deformities. Primary endpoint will be number of new ulcers incurred, defined as ulcers associated with hammer, mallet and claw toe deformities, placed on treated foot.

Secondary endpoints will be complications: infections (defined as ailment associated with procedure or ulcer, that is diagnosed as infection by attending health professional), transfer lesions (defined as impending ulcers or actual ulcers at anatomical sites associated with hammer, mallet and claw toes in patients with diabetes, on non-treated hammer, mallet and claw toes after surgical treatment), minor amputations (defined as amputations below ankle level), major amputations (defined as amputations at or above ankle level).

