5.2 Patients

Inclusion criteria

- Patients aged 18 years or above
- Type 1 or 2 diabetes
- Hammer, mallet or claw toe deformity
- Impending ulcer associated with above mentioned deformities
- Able to understand written and oral information
- Ability to follow planned visits and treatment
- Able to provide informed consent in Danish and/or English

Exclusion criteria

- Revascularization procedure in the affected limb planned, or undertaken within the 4 weeks prior to screening
- Hammer, mallet and claw toe that are rigid in both MTP, IP joints
- Ulcer associated with hammer, mallet and claw toe deformities
- Toe pressure < 30mmHg
- Prior major amputations on affected or ipsilateral leg
- Other corrective operation is indicated to treat patients foot deformities as deemed by investigator
- Current treatment with cytotoxic drugs or with systemically administered glucocorticoids
- Treatment of foot ulcers with growth factors, stem cells or equivalent preparations within the 8 weeks prior to screening
- Likely inability to comply with the need for planned visits because of planned activity
- Participation in another interventional clinical foot ulcer-healing trial within the 4 weeks prior to screening
- Prior enrolment in this trial
- Judgement by the investigator that the patient does not have the capacity to understand the study procedures or provide written informed consent

Discontinuation of patients

- Patient discontinues assigned treatment for any reason, while not fulfilling one of the studies accepted endpoints
- Participants who withdraw from treatment will be asked to remain in the trial for follow-up, and data will continue to be collected and analyzed.
- Patient incurs a serious adverse event (SAE), defined as death or sepsis related to the study procedure

- Investigator decides to discontinue patient due to health or compliance reasons
- Patient misses 3 consecutive visits
- Patient misses 5 or more visits during the full treatment period

Patients who discontinue the study early will be invited to have a clinical visit before being discontinued.

Patients that are discontinued will revert to their normal treatment plan, and continue in their respective clinics.

Endpoints

- New ulcer incurred
 - When/if new ulcer is incurred pictures will be send to two external evaluators to be confirmed as new ulcer
- Patient reaches 12 month visit without incurring a new ulcer

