- Patient incurs minor or major amputation on either treated or nontreated limb
- Patient receives surgical intervention relevant for the study (other than planned in study)

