5.4 Visit-plan

Patients in both the intervention and conservative groups will be expected to adhere to a specified visit-plan

Visit-plan Study IV	Inclusion	Day 0	Day 7	Day 14	End ¹	Follow-
						up ²
	0.1	a a b b	a	a a a i	2.0	2 0
Duration	3 hours	30 min	30 min	30 min	30	30 min
					min	
In/exclusion criteria	+					
Baseline blood samples and physical	+					
exam						
Patient history	+					
Foot Examination	+	+	+	+	+	+
Changes in Medicine/ new ailments			+	+	+	+
Toe systolic blood pressure (TSB)	+					
Ankle/brachial pressure index (ABPI)						
Neurological assessment	+					
Randomization	+					
Tenotomy/silicone spacer application ³		+				
Standard Care & offloading	+	+	+	+	+	+
Footwear assessment		$+^{4}$	+	+	+	+

1: This visit only happens if patient incurs on of the named endpoints

2: Follow-up visits are performed at 3, 6 and 12 months

- 3: Depending on allocated treatment
- 4: All Patients receive therapeutic sandals with individualized insole

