5.5.4 End

End visit is only performed if patients impending ulcer(s) has progressed to active ulcer(s), or impending ulcer has not progressed to active ulcer at 12 month visit.

- Foot examination
 - Inspection of pressure point, and deformities
 - o Pulses

- \circ Deformities
- \circ New Ulcers (not associated with registered impending ulcers at visit day 0
- Changes in medicine/new ailments
 - o Changes to the patient's medicine, and/or new diagnosis are registered
- Standard care & offloading
 - See section 5.3.2
- Impending ulcer
 - Has impending ulcer progressed to active ulcer
- Ulcer evaluation (if relevant)
 - Assessment of ulcer surroundings
 - Assessment of infection
 - o Assessment of healing
 - o Ulcer photo
 - o Measurement of longest length, width and depth in mm
 - Measurement of area in mm³(length*width*depth)
 - Assessment of incision site (where applicable)
 - o Measurement of length, width and depth of ulcer(s) after debridement
 - Categorizing by Texas Grading System
 - Footwear assessment
 - Footwear and/or current offloading is evaluated
 - Complications
 - Complications associated with tenotomy is registered (if relevant)
 - SAE is registered (if relevant)

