5.8 Statistics

All statistical analysis will be performed using the version of SAS currently used at our institute. All data will be analyzed on the intention to treat basis. All baseline data will be presented using appropriate summarizing statistics. Appropriate comparable statistical analysis will be applied to

- Incidence of new ulcer(s) in treated limb
- Mean time (in days) to healing of incision sites
- Incidence of minor amputations
- Incidence of major amputations

Odds-ratio will be applied to

- The incidence of secondary infection
- Pain in treated limb, associated with tenotomy
- Transfer lesion

Sample-size

The calculation is done with a Type 1 error rate (α) at 5%, and a power (1- β) at 80%. The primary endpoint is number of new ulcers incurred.

In the general diabetic population life time prevalence of diabetic ulcers has been reported at $15-25\%^{24}$, the yearly incidence in the same group is 6%. This study focuses on patients with a deformity reported to have a 1.5 hazard ratio²⁵, and signs of an impending ulcer like callus formation, which has been reported with a relative risk of 11^{26} . The incidence of new diabetic foot ulcers incurred by the study population is set at 10%, according to the above mentioned considerations.

The incidence in the intervention group (μ_A) is set at 6%, so the anticipated reduction in incidence is 4% compared to the incidence in the control group (μ_B) which as above mentioned is set at 10%. However, the numbers for incidence of new diabetic foot ulcers is an uncertain size, especially when looking at the specific group we are looking at, therefore the standard deviation (σ) is set at 10.

The calculator used is a 2 means, 2 sample, 2-sided equality calculator. The formula is

 $nB=(1+1/\kappa) ((\sigma z1-\alpha/2+z1-\beta)/(\mu A-\mu B))2$

nB= Sample size

 κ = The matching ratio

With the above described parameters, the sample size is 98 patients, which due to an expected dropout of 10% will be extended to 110 patients.

6. **Perspective**

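### Amputation on either limb is a named endpoint that can end observation of the treated foot, and the plan does not say how such a patient enters the primary analysis

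*Combined protocol and SAP*

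**What the plan says.** Section 4 states that the primary endpoint "will be number of new ulcers incurred, defined as ulcers associated with hammer, mallet and claw toe deformities, placed on treated foot". Minor and major amputations are secondary endpoints there.

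The endpoint list in 5.2 contains a new ulcer, for which "pictures will be send to two external evaluators to be confirmed as new ulcer"; arrival at the 12-month visit with no new ulcer; a further surgical intervention relevant to the study; and "Patient incurs minor or major amputation on either treated or nontreated limb". The discontinuation list in the same section counts stopping the assigned treatment as discontinuation only if no accepted endpoint has been met.

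Two places say what triggers the End visit. Footnote 1 of 5.4 reads: "This visit only happens if patient incurs on of the named endpoints". Section 5.5.4 reads: "End visit is only performed if patients impending ulcer(s) has progressed to active ulcer(s", or if progression has not occurred by the 12-month visit. Amputation does not appear in 5.5.4.

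Section 5.8 calls for intention-to-treat analysis by appropriate methods. It lists new ulcers in the treated limb and, as separate items, "Incidence of minor amputations" and the same for major amputations. It has no rule for a patient whose observation stops at an amputation.

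**The concern.** The primary outcome belongs to one foot, but an event on the other foot is listed as an endpoint of the study. An other-limb amputation does not show whether the treated foot has ulcerated or will ulcerate. If it closes the patient's observation, the remaining treated-foot follow-up is lost. The loss may also be informative, since a patient who needs an amputation is probably not at average risk of ulceration.

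An amputation of the treated foot or toe raises a different problem. Confirmation of an ulcer depends on pictures sent to external evaluators. If the tissue is removed before an ulcer has been photographed, the primary endpoint can no longer be confirmed at that site. The plan does not say whether that patient is an event, censored, a competing event, missing or ulcer-free. With few events expected, a choice made after the data are seen could affect the result.

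**Working it through.** **The passages side by side**

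| Question | 5.2 | 5.4, footnote 1 | 5.5.4 | 5.8 |
|---|---|---|---|---|
| Is amputation a named endpoint? | Yes, either limb | Refers to the named endpoints | Not mentioned | Analysed as separate items, limb not stated |
| Does it trigger the End visit? | Not stated | Yes, as a named endpoint | No | Not stated |
| Does treated-foot follow-up continue? | Only for those who withdraw from treatment | Not stated | Not stated | Not stated |
| How is it scored for the primary endpoint? | Not stated | Not stated | Not stated | Not stated |

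The footnote and 5.5.4 cannot both describe the End visit. On the footnote's reading an amputation on either limb leads to it. On the 5.5.4 reading neither does. The eligibility criteria bear on this too: prior major amputation is an exclusion only for the affected or ipsilateral leg. A patient with an earlier contralateral amputation can therefore enter and be followed, so ending observation for a new contralateral amputation has no evident purpose.

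**The plan's own sample size**

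Inputs from 5.8: two-sided alpha 5%, power 80%, incidences 10% and 6% (difference 4 points), standard deviation 10. An allocation ratio of 1 is assumed because none is given.

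n = 2 × (10 × (1.960 + 0.842) / 4)² = 98.11

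This reproduces the stated 98. The formula returns a size per arm, while the plan uses 98 as the whole sample. Both readings are carried below: 49 per arm (98 / 2) and 98 per arm. The point does not depend on which is right.

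**Expected primary events**

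- 49 per arm: control 49 × 0.10 = 4.9; intervention 49 × 0.06 = 2.94; difference 1.96 patients.
- 98 per arm: control 98 × 0.10 = 9.8; intervention 98 × 0.06 = 5.88; difference 3.92 patients.

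**Illustration: one event lost or mis-scored**

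The number of such events is an assumption. The patient stays in the denominator.

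| | 49 per arm | 98 per arm |
|---|---|---|
| One control event lost: control rate | 3.9 / 49 = 8.0% | 8.8 / 98 = 9.0% |
| Difference from 6% | 2.0 points | 3.0 points |
| One intervention event lost: intervention rate | 1.94 / 49 = 4.0% | 4.88 / 98 = 5.0% |
| Difference from 10% | 6.0 points | 5.0 points |

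If the control patient is instead dropped from the denominator, the rates are 3.9 / 48 = 8.1% and 8.8 / 97 = 9.1%, so the differences are 2.1 and 3.1 points. The result is nearly the same.

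**One lost event is not one lost patient**

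At the planned control rate, stopping observation of one control patient removes at most 0.10 expected events. It removes more only if amputees have a higher ulcer risk than the plan assumes, which is plausible but not quantified in the documents. One patient equals one event only where a qualifying ulcer on the treated foot went unconfirmed.

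**The case against.** The strongest reply has four parts.

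- **Exit is inferred.** Footnote 1 triggers a visit and does not say that observation stops, and no text cancels the 3, 6 and 12-month visits after an amputation. Under 5.5.4 the problem would not arise. This stands as a caution, and so the conclusion is that amputation *can* end observation. It does not remove the contradiction. The instruction to keep following patients is written for those who withdraw from treatment, not for those who reach an endpoint. Intention to treat does not supply outcomes that were never observed.
- **Amputees are not scored ulcer-free.** A reader might infer that they are. The documents do not say so: the ulcer-free endpoint requires reaching the 12-month visit, and amputation is a separate entry. This stands. What remains is the lack of any rule.
- **Most relevant amputations would already be counted.** Section 1 reports that "85% of all amputations are performed due to a diabetic ulcer", and 5.2 excludes patients with a deformity-associated ulcer at entry. An ulcer leading to amputation would therefore usually be new and, if deformity-associated and on the treated foot, already a primary event. Patients who ulcerate between day 14 and month 3 are told to contact staff. This stands and narrows the treated-foot exposure to ulcers not confirmed before amputation. The instruction to make contact is not written for months 3 to 12.
- **Harm is not hidden, and limbs are not shown to be pooled.** A reader might infer both. Amputations are secondary endpoints with their own comparisons, and tenotomy complications are recorded at visits. Section 5.8 is silent on limb; it does not say that both limbs are combined. Both objections stand.

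**Conclusion.** The concern holds in this form: 5.2 and footnote 1 of 5.4 together allow an amputation on either limb, including the one that the primary endpoint ignores, to end observation of the treated foot. Section 5.5.4 contradicts this. The plan has no rule for a patient who exits at amputation without a confirmed ulcer.

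The documents give no amputation rate, so neither the number of patients affected nor the direction of any bias can be estimated. The shift from 4 points to about 2 (49 per arm) or 3 (98 per arm) is the effect of one lost control event under the planned incidences and equal allocation; it is not a forecast. It shows that an outcome with about 5 to 10 expected control events has little tolerance for unplanned exits or for scoring decided late. The documents do not support the stronger claim that treatment failures will be counted as successes.

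**What to change.** 1. **5.2, 5.4 and 5.5.4:** reconcile the endpoint list, footnote 1 and the End-visit description so that they agree on whether amputation triggers the End visit and whether that visit closes observation.
2. **5.2 and 5.4:** state that an amputation on the other limb does not end follow-up of the treated foot, which continues at the existing visits to 12 months. This concerns data collection only, not treatment.
3. **5.8:** state, before outcome data are seen, that an amputation of the treated foot without a previously confirmed ulcer is not counted as ulcer-free. Treat it as a competing event or as missing in the main analysis, with a sensitivity analysis that counts it as a failure. The reverse order is defensible if the sponsor prefers a composite. The composite has a price: it admits amputations from causes outside the primary definition.
4. **5.8:** report minor and major amputations by limb.

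The further-surgery entry in the 5.2 endpoint list has the same gap and can be covered by the same wording.

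The cost is a few sentences, some visits already in the schedule for a few patients, and one more sensitivity analysis. No additional patients are needed.

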7.2 Personal data usage and protection

The appropriate approval from the Danish data protection agency will be obtained before the study commences, and their guidelines will be followed throughout the process. All patient data will be stored and treated in accordance with regulation 2016/679 from the European parliament on the protection of natural persons with regard to the processing of personal data and on the free movement of such data, dated 27 April 2016²⁹, and the Danish amendment to regulation 2016/679³⁰.

7.3

Patient Perspective and Conclusion

Patients enrolled in this study will receive a treatment that is already implemented in our and several other clinics, and the unpublished data from our retrospective study and the formerly published data on tenotomies, points towards tenotomies being a safe and effective treatment of hammer, mallet and claw toes. Patients who don't receive intervention in the form of tenotomies in the study, will receive standard offloading and ulcer treatment, and be offered to undergo tenotomy if an ulcer occurs and tenotomi is found relevant. In conclusion the patients enrolled in the study will receive a treatment with potential benefits for them, and a low risk of complications making the study ethically sound.

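### The protocol conflicts on whether off-plan surgery before an ulcer ends follow-up, and the intention-to-treat analysis has no rule for such patients

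*Combined protocol and SAP*

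**What the plan says.** Four places in the protocol bear on this.

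- **Section 5.2, Endpoints.** The list contains a new ulcer, an amputation on either limb, and "Patient receives surgical intervention relevant for the study (other than planned in study". It also contains "Patient reaches 12 month visit without incurring a new ulcer". Since completing the trial is on the list, it works as a list of ways to finish, not only of outcomes.
- **Section 5.4, footnote 1 to the End visit.** "This visit only happens if patient incurs on of the named endpoints".
- **Section 5.5.4, on the End visit.** It is held in two cases only: when an impending ulcer has become an active one, or when month 12 arrives with no such change. Surgery is not mentioned.
- **Section 5.2, Discontinuation.** One bullet reads "Patient discontinues assigned treatment for any reason, while not fulfilling one of the studies accepted endpoints". The next reads "Participants who withdraw from treatment will be asked to remain in the trial for follow-up, and data will continue to be collected and analyzed".

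Section 4 defines the primary endpoint as new ulcers only. On analysis, section 5.8 states "All data will be analyzed on the intention to treat basis". It lists the incidence of new ulcers in the treated limb, with no rule for a patient who has off-plan surgery first.

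**The concern.** Off-plan surgery happens after randomization and is not the primary outcome. If it closes a patient's participation, ulcer status at month 12 is unknown for that patient, and the comparison of everyone as allocated over 12 months is incomplete.

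The loss is unlikely to be random. Surgery before an ulcer would plausibly be done because an impending ulcer is worsening. The reasons may also differ by arm: a first tenotomy in a control, or further surgery for a transfer lesion (which section 4 anticipates) after tenotomy. The treatments are surgery and offloading, with no blinding of patients or clinicians described. Section 7.3 says "Patients enrolled in this study will receive a treatment that is already implemented in our and several other clinics", so the procedure is at hand.

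Few events are expected. With 110 patients split equally (the allocation ratio is not given, so 55 per arm is an assumption), the planned incidences imply 55 × 10% = 5.5 ulcers against 55 × 6% = 3.3. The status of two or three patients matters at that scale.

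**Working it through.** **Step 1: does follow-up stop?** Sections 5.2 (Endpoints) and 5.4 (footnote 1), read together, say that off-plan surgery is a named endpoint and that a named endpoint leads to the End visit. The visit table prints the follow-up column after the End column, but no text says that the 3, 6 and 12-month visits continue once an End visit has taken place. Section 5.5.4 allows the End visit only for ulcer progression or for month 12 without progression, so on that text surgery is not a trigger. The retention sentence could keep the patient in follow-up. However, the bullet before it concerns patients who have not met an accepted endpoint, and a patient with off-plan surgery has met one. The texts do not resolve each other.

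**Step 2: how would the patient count?** Section 5.8 does not say whether such a patient is an ulcer, no ulcer, censored or missing.

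**Step 3: what could it do to the result?**

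Inputs from section 5.8: control incidence 10%, intervention incidence 6%, planned difference 10 − 6 = 4 points.

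Assumptions, because the documents give none of these:
- a share c of controls has off-plan surgery before any ulcer;
- without surgery their 12-month ulcer risk would be r;
- surgery multiplies that risk by 6/10 = 0.6, the planned effect;
- the intervention arm stays at 6%.

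Formulas for control incidence:
- full follow-up: 10 − c·r + 0.6·c·r
- follow-up stopped, scored ulcer-free: 10 − c·r
- loss from stopping: 0.6·c·r

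Example, c = 5% and r = 50%: c·r = 2.5 points. Full follow-up gives 10 − 2.5 + 1.5 = 9.0%, a difference of 3.0. Scored ulcer-free gives 7.5%, a difference of 1.5.

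Example, c = 5% and switchers at three times the risk of other controls: other controls have 10/(0.95 + 0.05 × 3) = 9.09%, so r = 27.3%.

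| c | r | Full follow-up: control, difference | Scored ulcer-free: control, difference | Loss (points) |
|---|---|---|---|---|
| 2% | 10% | 9.92%, 3.92 | 9.80%, 3.80 | 0.12 |
| 2% | 50% | 9.60%, 3.60 | 9.00%, 3.00 | 0.60 |
| 5% | 10% | 9.80%, 3.80 | 9.50%, 3.50 | 0.30 |
| 5% | 27.3% | 9.45%, 3.45 | 8.64%, 2.64 | 0.82 |
| 5% | 50% | 9.00%, 3.00 | 7.50%, 1.50 | 1.50 |

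At 55 per arm, 5% is about 3 controls and 2% about 1.

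Excluding switchers gives (10 − c·r)/(1 − c). At c = 5% this is 10.0% for r = 10% (difference 4.0, above the 3.8 with full follow-up) and 7.5/0.95 = 7.9% for r = 50% (difference 1.9, below 3.0). The direction therefore depends on the counting rule and on the switchers' risk.

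**The case against.** The strongest reply is that no sentence says follow-up stops after off-plan surgery. Section 5.5.4 leaves surgery out of the End triggers, and the retention sentence points towards keeping such patients. This stands. A reader might infer that a control who has a tenotomy simply leaves the trial and that intention to treat is thereby broken. The documents support only that the texts can be read that way and conflict.

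Second, section 7.3 plans to offer controls tenotomy only once an ulcer has occurred, when it can no longer affect whether a first ulcer is counted. Section 5.2 also excludes patients for whom another corrective operation is indicated. Both make early surgery less likely. Neither rules it out, and the sponsor foresaw it well enough to list it.

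Third, the illustration rests on assumed inputs. The 50% risk at 5% switching is high: other controls would then have 7.5/95 = 7.9%, so switchers carry about six times their risk. With equal risk (r = 10%) the loss is only 0.3 points at 5% switching and 0.12 at 2%. This stands, and is why a range is shown.

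Fourth, a reader might infer that off-plan surgery would be scored as a primary event and inflate the control incidence (at c = 5% and r = 50%: 7.5 + 5 = 12.5%, a difference of 6.5). No text supports this. Section 4 counts ulcers only, and section 5.2 sends new ulcers to two external evaluators for confirmation.

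Finally, following patients through surgery is one legitimate strategy among several. It is, however, the one that fits the plan's own commitments to intention to treat and retention.

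**Conclusion.** The point holds as a conflict in the follow-up rules together with a gap in the analysis plan. Sections 5.2, 5.4 and 5.5.4 do not agree on whether off-plan surgery ends data collection, and section 5.8 does not say how these patients enter the primary analysis. Sites could apply the rules differently, and the counting choice could be made after the data are seen.

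If follow-up stops, the primary ulcer incidence can be biased. That it will be, or in which direction, cannot be concluded: this depends on the switching rate, the switchers' risk and the counting rule, none of which is given. With 5% of controls switching at about three to six times the risk of other controls, the difference is about 3.0 to 3.5 points under full follow-up and 1.5 to 2.6 if switchers are stopped and scored ulcer-free. At 2% switching the loss is about 0.1 to 0.6 points. Unequal loss between arms is plausible but not stated; the listed endpoint applies to both.

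The correction is worth making because ulcer status that was not collected cannot be recovered later.

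**What to change.** Reconcile section 5.2, footnote 1 in section 5.4 and section 5.5.4 so that off-plan surgery does not end data collection. Specifically:

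- A patient who has foot surgery outside the plan, in either arm, keeps the scheduled visits to month 12.
- That patient is analysed in the allocated arm for the primary ulcer endpoint, whatever surgery was received. State this in section 5.8.
- Record the date, toe and reason for the surgery, and report it by arm.
- Add one sensitivity analysis in which the event is an ulcer or off-plan surgery, whichever comes first.
- Apply the same follow-up rule to amputations on the same list that leave the treated foot assessable, such as those on the non-treated limb.

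The cost is protocol wording plus already scheduled 30-minute visits for a few patients. The downside is some dilution of the effect by switching: 0.4·c·r, or 0.05 × 50% × 0.4 = 1.0 point in the most extreme case shown. The change concerns data collection and analysis only, not which surgery a patient should receive or when.
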